9.2. Randomization and Registration of Subjects

Subjects will be registered and randomized at Day 1, after all baseline assessments have been completed. In particular, prior to randomization at Day 1, the Investigator must verify that the subjects are eligible according to criteria in Section 8.1 and Section 8.2 (including confirmation of DaT deficit by central reader) and that the MDS-UPDRS results from Day 1 are available. No subject may begin treatment prior to assignment of a unique identification number (registration) and randomization. The identification number will be used on study-related documents pertaining to the subject. Any subject identification numbers that are assigned will not be reused even if the subject does not receive treatment.

CONFIDENTIAL

The information contained herein may not be used, disclosed, or published without the written consent of Biogen MA Inc.

Subjects will be randomized at Day 1 into 1 of 4 parallel dosing arms to receive placebo or BIIB054 (250 mg, 1250 mg, and 3500 mg). Cohort A (approximately 24 subjects) will be enrolled and randomized first in a 1:1:1:1 ratio. Randomization and dosing for Cohort B (approximately 287 subjects) will start after all subjects in Cohort A complete Week 12 assessments, and all available safety and PK data are reviewed by the IDMC. Randomization of subjects in Cohort B will be stratified by baseline (Day 1) MDS-UPDRS Part I + II + III total scores (≤ 35 and >35) and striatum SBR (≤ 1.2 and >1.2), and subjects will be randomized at Day 1 into 1 of 4 parallel dosing arms to receive placebo (n=82) or BIIB054 (250 mg [n=41], 1250 mg [n=82], or 3500 mg [n=82]) in each stratum.

All subjects who were randomized to receive placebo in Year 1 will be randomized, in equal ratio, to 1 of the active BIIB054 treatments for Year 2. For subjects receiving placebo in Cohort A, this randomization will occur prior to Infusion 14; for subjects receiving placebo in Cohort B, this randomization will occur at the time of the baseline Day 1 randomization (Year 1). Subjects who received BIIB054 (1250 mg or 3500 mg) in Year 1 will continue with the same dose regimen in Year 2. In addition, the decision of whether to randomize subjects who receive the 250-mg dose in Year 1 to 1 of the 2 highest doses of BIIB054 in Year 2 will be made after the IDMC review of Cohort A Week 12 data.

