11.1.2. Years 2 through 4 (Active-Treatment Dose-Blinded Portion of the Study)

Prior to Infusion 14 (first dose of Year 2), subjects who received placebo in Year 1 will be randomized to 1 of the active-treatment arms for Year 2; these subjects will receive BIIB054 in Years 2 through 4. Subjects who received BIIB054 (250, 1250, or 3500 mg) in Year 1 will continue to receive the same dose regimen of BIIB054 in Years 2 through 4.

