16.5.2.1. Year 1 (Placebo-Controlled Portion of the Study)

The changes in clinical function, including motor [REDACTED] (MDS-UPDRS, [REDACTED]) [REDACTED] outcome measures will be included in the analyses in Year 1 (Week 52).

Analyses of these endpoints will be performed in the ITT population, with select endpoints (e.g., MDS-UPDRS) also analyzed using the per protocol population.

Changes from baseline in the primary endpoint MDS-UPDRS Part I + II + III total scores at Week 52 will be analyzed using the MMRM. The model may include fixed effect of treatment group, baseline MDS-UPDRS I + II + III total score values, region, PD subtype, baseline DaT/SPECT striatum SBR values, visit, and the interaction terms between treatment and visit, between baseline MDS-UPDRS I + II + III total score by visit, and between baseline DaT/SPECT striatum SBR values and visit. The correlation between repeated measures of the outcomes will be taken into consideration in the model. Dose-response relationship will be tested based on the MCP-MOD method (potential candidate models will include linear, linear-log, quadratic, maximum effect (E_{max}), and logistic models, as specified in Section 16.9). A multiple comparison adjustment method will be applied to control the overall type I error at 0.05 in the study, due to the primary endpoint of MDS-UPDRS total score being analyzed at Week 52 and Week 72, and superiority against placebo is considered reached in study if statistically significant result is achieved at either timepoint. The details of the multiple comparison adjustment method will be pre-specified in the SAP. Pairwise comparison of each active group versus placebo will also be conducted, however, no additional multiplicity adjustment will be made, and nominal p-values will be reported.

Secondary endpoints, e.g., change from baseline in the MDS-UPDRS subscores (e.g., Part I, II, or III score, Part II and III total score) will be analyzed in a similar model, but no additional multiplicity adjustment will be made or for other secondary endpoints. Additional details will be provided in the SAP.

[REDACTED]

[REDACTED] Cox's

CONFIDENTIAL

The information contained herein may not be used, disclosed, or published without the written consent of Biogen MA Inc.

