proportional hazard model will be used to analyze the data, where appropriate. The model may adjust for baseline MDS-UPDRS values, region, PD subtype, baseline Modified Hoehn and Yahr stage, prior usage status of symptomatic PD medication, and baseline DaT/SPECT striatum SBR values. If the proportionality assumption does not hold, the log rank test will be used. More details will be described in the SAP.

16.5.2.2. Years 2 through 4 (Active-Treatment Dose-Blinded Portion of the Study) and Overall Experience

At Week 72, the primary endpoint of changes from baseline in MDS-UPDRS Part I + II + III total scores will be analyzed using the MMRM, similar to the Year 1 analyses with similar covariates in the model. The treatment groups included in the model will be the delayed start/initiation group (placebo to BIIB054), and the immediate start/initiation groups (the original 250 mg, 1250 mg and 3500 mg BIIB054 groups). Dose response relationship will be tested based on the MCP-MOD method (potential candidate models will include linear, linear-log, quadratic, E_{max} , and logistic models, as specified in Section 16.9). A multiple comparison adjustment method will be applied to control the overall type I error at 0.05 in the study, due to the MDS-UPDRS Part I + II + III total score being analyzed at Week 52 and Week 72 and success of efficacy is considered at either timepoint. The details of the method will be pre-specified in the SAP. The results of the analysis will be considered statistically significant after applying the multiple comparison adjustment method. Pairwise comparison of each immediate start group versus the delayed start group will also be conducted; however, no additional multiplicity adjustment will be made, and nominal p-values will be reported.

Secondary endpoints, e.g. change from baseline in the MDS-UPDRS subparts (e.g., Part I, II, or III, IV score, Part II and III total score) or change in MDS-UPDRS I + II + III total score at end of study, will be analyzed in a similar model, but no additional multiplicity adjustment will be made for secondary endpoints.

[REDACTED]

[REDACTED]

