16.8. Interim Analyses

Safety and PK data only will be reviewed by the IDMC after subjects in Cohort A have completed Week 12 Visit assessments, and before dosing any subjects in Cohort B.

After subjects in Cohort A complete the Week 24 Visit, [REDACTED], all available serum PK, [REDACTED] from [REDACTED] Cohort A will be analyzed by a statistical/PK team independent of the study. The grouped level summary statistics will be reviewed only by a limited number of individuals at Biogen who are not involved in the management of the subjects or subject-level data for the study. No changes to the study design are expected based on this review.

For the purpose of planning for future studies, an administrative interim analysis may be performed when approximately 60% of the subjects have completed the Week 52 Visit. A small unblinded team from Biogen, separate from the study management team, will have access to the unblinded interim analysis results.

A full analysis of the 1-year data will be performed after all subjects have completed the Week 52 Visit. A small unblinded team from Biogen, separate from the study management team, will have access to the unblinded 1-year analysis results.

An interim analysis when all subjects have completed the Week 72 Visit is planned to be conducted. A small unblinded team from Biogen, separate from the study management team, will have access to the unblinded interim analysis results.

A multiple comparison adjustment method will be applied to control the overall type I error at 0.05 in the study, due to the primary endpoint of change from baseline in MDS-UPDRS total score being analyzed at Week 52 and Week 72, and superiority against placebo is considered reached in the study if statistically significant result is achieved at either timepoint at the respective adjusted alpha-level. The details of the multiple comparison adjustment method will be pre-specified in the SAP. No additional multiplicity adjustments will be made for secondary or exploratory endpoint analyses.

CONFIDENTIAL

The information contained herein may not be used, disclosed, or published without the written consent of Biogen MA Inc.

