16.9. Sample Size Considerations

The sample size calculation is based on changes in MDS-UPDRS Part I + II + III total score at Week 52 and at Week 72 of treatment. Based on data from the Parkinson's Progression Markers Initiative study, the placebo subject's mean and standard deviation (SD) at Week 52 and Week 72 are assumed to be 8.0 (10.64) and 9.6 (13.7) respectively. Assuming a maximum of 55% reduction in the change from baseline in the active group with maximum response relative to placebo group, the mean (SD) for this active group will be 3.2 (10.64) and 3.84 (13.7) respectively at Week 52 and Week 72, and the responses for other active groups are assumed to be somewhere between 0 and the maximum response. The primary analysis will be based on the MCP-MOD method to detect a dose-response trend while controlling for multiplicity. Optimal contrasts will be constructed to detect potential dose-response trend under common dose-response curves (e.g., E_{\max} , exponential, logistic, linear in log dose, and quadratic model, which are illustrated with parameters shown in [Figure 5](#) which will be used for both Week 52 and Week 72). The planned enrollment is 311 subjects total (24 subjects in Cohort A and 287 subjects in Cohort B, [Table 8](#)). Actual enrollment is 357 subjects. In Cohort A, 29 subjects were randomized in a 1:1:1:1 ratio to each of the treatment groups, while in Cohort B 328 subjects were randomized in 2:1:2:2 ratio to the placebo, 250 mg, 1250 mg, and 3500 mg groups. Based on the actual enrollment, the estimated number of subjects by cohort and treatment groups are given in [Table 9](#) below. After accounting for dropout rate of 10% and 15% at Week 52 and Week 72, respectively, the estimated sample sizes are given in [Table 10](#) and [Table 11](#). With the updated sample size, the study will provide an average power of approximately 80% to detect the dose-response trend over 1 year of treatment, based on a 2-sided type I error of 0.05 and approximately 73% of power at the Week 72 analyses, based on a 2-sided type I error of 0.05. Overall, the sample size in the study will provide approximately 89% power. If there are any modifications to the candidate dose-response curves/models or parameters, the final candidate models for the MCP-MOD will be prespecified and described in the SAP.

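### A Week 72 result alone can be declared superiority against placebo, although the Week 72 comparator is a delayed-start arm, and the 73% Week 72 power silently assumes that this arm gains nothing from BIIB054

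*Protocol*

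**What the plan says.** - **The switch.** Protocol 11.1.2: "subjects who received placebo in Year 1 will be randomized to 1 of the active-treatment arms for Year 2". Section 9.2 adds that they "will be randomized, in equal ratio, to 1 of the active BIIB054 treatments for Year 2". The first active dose is Infusion 14, at Week 52.
- **The Week 72 model.** Section 16.5.2.2: "The treatment groups included in the model will be the delayed start/initiation group (placebo to BIIB054"), set against the three groups that received BIIB054 from the start. This section words its success rule without naming placebo.
- **The success rule elsewhere.** Section 16.5.2.1: "superiority against placebo is considered reached in study if statistically significant result is achieved at either timepoint". Section 16.8: "superiority against placebo is considered reached in the study if statistically significant result is achieved at either timepoint at the respective adjusted alpha-level".
- **The power.** Section 16.9 takes from an external observational cohort a placebo "mean and standard deviation (SD) at Week 52 and Week 72 are assumed to be 8.0 (10.64) and 9.6 (13.7) respectively", and assumes a maximum 55% reduction relative to placebo at both visits. It states about 80% power at Week 52, 73% at Week 72 (each at two-sided 0.05) and 89% overall.

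**The concern.** The visit that can decide the trial on its own has no placebo group. A positive Week 72 test shows that starting BIIB054 a year earlier gives a better result at Week 72. That is worth knowing, but it is a different statement from superiority over placebo, and two sections attach the second statement to it.

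The power has the same gap. The calculation lets the control arm worsen from 8.0 to 9.6 between Weeks 52 and 72 while all of its subjects are on BIIB054. The assumed best-dose difference therefore widens over 20 weeks in which every arm is treated. That can happen only if the drug does nothing in the delayed-start arm during that time. Section 16.9 neither states nor defends this. At stake are the wording of the main efficacy conclusion and the honesty of two of the three power figures.

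**Working it through.** **Exposure of the control arm at Week 72.** Table 4 schedules infusions at Weeks 52, 56, 60, 64 and 68. The Week 72 MDS-UPDRS is done before that day's infusion, so five BIIB054 infusions precede it.

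**Inputs (16.9 and Table 11).** Placebo mean 8.0 at Week 52 and 9.6 at Week 72; SD 13.7 at Week 72; 86, 46, 86 and 86 subjects on placebo, 250, 1250 and 3500 mg; two-sided 0.05; maximum reduction 55%. The printed best-dose means (3.2 and 3.84) correspond to 60%, since 1 − 3.2/8.0 = 1 − 3.84/9.6 = 0.60. Both readings are checked.

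**Reproducing the 73%.** Best dose against control, SE = 13.7 × √(2/86) = 2.089, power = Φ(difference/SE − 1.96):

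- 55%: difference 0.55 × 9.6 = 5.28; 5.28/2.089 = 2.527; power 71.5%.
- 60%: difference 9.6 − 3.84 = 5.76; 5.76/2.089 = 2.757; power 78.7%.

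The MCP-MOD maximum-contrast test was simulated with optimal contrasts. The Figure 5 parameters are not visible, so five assumed sets of candidate shapes were used. Average power is 73 to 77% at 55% and 81 to 83% at 60%. The stated 73% therefore fits the 55% effect against a control that has not been switched.

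**Letting the control arm respond from Week 52.** Control mean at Week 72 = 9.6 − 1.6 × r × g. Here 1.6 = 9.6 − 8.0, r is the maximum reduction, and g is the average fraction of the maximum effect over the three doses (equal thirds).

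- r = 0.55, g = 1: control mean 9.6 − 0.88 = 8.72; best-dose mean 9.6 × 0.45 = 4.32; difference 4.40. This equals the Week 52 difference, 0.55 × 8.0. Power: 4.40/2.089 = 2.106, giving 55.8%.
- r = 0.60, g = 1: control mean 8.64; difference 8.64 − 3.84 = 4.80; 4.80/2.089 = 2.297; power 63.2%.

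MCP-MOD average power at 55%, same five shape sets:

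| Delayed-start arm by Week 72 | Week 72 power |
|---|---|
| No benefit (as in 16.9) | 73–77% |
| Average effect of the three doses | 64–70% |
| Maximum effect in every switched subject | 59–65% |
| Half of the Year 1 difference lost (partial catch-up) | 17–20% |

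Four further assumed shape sets gave 75–77%, 67–70% and 62–64% for the first three rows.

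**Overall power.** Probability of success at either visit = 1 − Φ₂(−z(0.80), −z(P72); ρ), where P72 is the Week 72 power. With P72 = 0.73, ρ = 0.5 gives 89.3%, matching the stated 89%, so ρ = 0.5 is used below. P72 = 0.55, 0.60, 0.65 and 0.70 then give 85.2%, 86.2%, 87.3% and 88.5%.

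All of these figures precede any multiplicity adjustment, whose method the protocol leaves to the SAP.

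**The case against.** Section 16.5.2.2, which governs the Week 72 analysis, names the comparator correctly and does not claim superiority over placebo. On that view the analysis is properly specified, and the phrase in 16.5.2.1 and 16.8 is loose shorthand for the arm originally randomised to placebo. This stands in part: the model needs no change. It does not excuse the success rule, because the conclusion is where the comparator has to be exact, and the protocol now words that conclusion in two ways.

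A reader might infer that the Week 72 test is invalid or inflates the type I error. The documents do not support that. The groups compared are those randomised at Day 1; if BIIB054 has no effect they do not differ, and if it helps, treating the controls shrinks the contrast and makes a Week 72 success harder.

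A reader might also infer that 73% is simply wrong. It is not, if the effect takes more than 20 weeks to appear, which is a possible planning assumption for a drug meant to slow progression. The fault is that the assumption goes unstated.

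Finally, no section says that the delayed-start group enters the Week 72 MCP-MOD at dose zero. That is a plausible inference, since 16.9 uses the same Figure 5 curves at both visits, but final candidate models may be given in the SAP.

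**Conclusion.** The point holds in two parts. First, 16.5.2.1 and 16.8 permit a conclusion against placebo from a contrast that 16.5.2.2 correctly describes as immediate against delayed start. This is a contradiction in the text and rests on no assumption. Second, the 73% and 89% are upper-case figures that require no BIIB054 benefit in the delayed-start arm by Week 72.

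The size of the second part is conditional. With the plan's 55% effect acting from Week 52, Week 72 power is about 60 to 70% by MCP-MOD (about 56% pairwise). Overall power is about 85 to 87% for Week 72 power of 55 to 65%, and 88.5% at the top of the range. These values depend on assumed shapes in place of Figure 5 and on a between-visit correlation of 0.5 inferred from the stated 89%. They are illustrative and should not be copied into the protocol. Partial catch-up would take Week 72 power far lower. The Week 52 test and its stated 80% are unaffected.

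**What to change.** 1. In 16.5.2.1 and 16.8, limit the claim of superiority against placebo to the Week 52 test. Define a Week 72-only success as immediate start superior to delayed start, in line with 16.5.2.2.
2. In 16.9, state that 73% assumes no benefit in the delayed-start arm by Week 72 and is the upper case. Restate Week 72 and overall power for a control split equally over the three doses, using the actual Figure 5 shapes, and include a catch-up case.
3. If the delayed-start group is entered at dose zero in the Week 72 MCP-MOD, label it as delayed start and take the dose-response estimate against placebo from Week 52.

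The cost is some wording and one recalculation, best completed before Week 72 results are unblinded. The stated power becomes less favourable; conduct, sample size and the test itself do not change.

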16.8. Interim Analyses

Safety and PK data only will be reviewed by the IDMC after subjects in Cohort A have completed Week 12 Visit assessments, and before dosing any subjects in Cohort B.

After subjects in Cohort A complete the Week 24 Visit, [REDACTED], all available serum PK, [REDACTED] from [REDACTED] Cohort A will be analyzed by a statistical/PK team independent of the study. The grouped level summary statistics will be reviewed only by a limited number of individuals at Biogen who are not involved in the management of the subjects or subject-level data for the study. No changes to the study design are expected based on this review.

For the purpose of planning for future studies, an administrative interim analysis may be performed when approximately 60% of the subjects have completed the Week 52 Visit. A small unblinded team from Biogen, separate from the study management team, will have access to the unblinded interim analysis results.

A full analysis of the 1-year data will be performed after all subjects have completed the Week 52 Visit. A small unblinded team from Biogen, separate from the study management team, will have access to the unblinded 1-year analysis results.

An interim analysis when all subjects have completed the Week 72 Visit is planned to be conducted. A small unblinded team from Biogen, separate from the study management team, will have access to the unblinded interim analysis results.

A multiple comparison adjustment method will be applied to control the overall type I error at 0.05 in the study, due to the primary endpoint of change from baseline in MDS-UPDRS total score being analyzed at Week 52 and Week 72, and superiority against placebo is considered reached in the study if statistically significant result is achieved at either timepoint at the respective adjusted alpha-level. The details of the multiple comparison adjustment method will be pre-specified in the SAP. No additional multiplicity adjustments will be made for secondary or exploratory endpoint analyses.

CONFIDENTIAL

The information contained herein may not be used, disclosed, or published without the written consent of Biogen MA Inc.

A blinded sample size re-estimation may be conducted when approximately 10% of subjects have completed the Week 52 Visit or approximately 1 month before enrollment is projected to be completed, whichever is earlier. The study sample size may be increased based on this blinded data review. There may be small adjustments to the percentage depending on actual enrollment rate. Details will be provided in the SAP.

16.9. Sample Size Considerations

The sample size calculation is based on changes in MDS-UPDRS Part I + II + III total score at Week 52 and at Week 72 of treatment. Based on data from the Parkinson's Progression Markers Initiative study, the placebo subject's mean and standard deviation (SD) at Week 52 and Week 72 are assumed to be 8.0 (10.64) and 9.6 (13.7) respectively. Assuming a maximum of 55% reduction in the change from baseline in the active group with maximum response relative to placebo group, the mean (SD) for this active group will be 3.2 (10.64) and 3.84 (13.7) respectively at Week 52 and Week 72, and the responses for other active groups are assumed to be somewhere between 0 and the maximum response. The primary analysis will be based on the MCP-MOD method to detect a dose-response trend while controlling for multiplicity. Optimal contrasts will be constructed to detect potential dose-response trend under common dose-response curves (e.g., E_{\max} , exponential, logistic, linear in log dose, and quadratic model, which are illustrated with parameters shown in [Figure 5](#) which will be used for both Week 52 and Week 72). The planned enrollment is 311 subjects total (24 subjects in Cohort A and 287 subjects in Cohort B, [Table 8](#)). Actual enrollment is 357 subjects. In Cohort A, 29 subjects were randomized in a 1:1:1:1 ratio to each of the treatment groups, while in Cohort B 328 subjects were randomized in 2:1:2:2 ratio to the placebo, 250 mg, 1250 mg, and 3500 mg groups. Based on the actual enrollment, the estimated number of subjects by cohort and treatment groups are given in [Table 9](#) below. After accounting for dropout rate of 10% and 15% at Week 52 and Week 72, respectively, the estimated sample sizes are given in [Table 10](#) and [Table 11](#). With the updated sample size, the study will provide an average power of approximately 80% to detect the dose-response trend over 1 year of treatment, based on a 2-sided type I error of 0.05 and approximately 73% of power at the Week 72 analyses, based on a 2-sided type I error of 0.05. Overall, the sample size in the study will provide approximately 89% power. If there are any modifications to the candidate dose-response curves/models or parameters, the final candidate models for the MCP-MOD will be prespecified and described in the SAP.

With an estimated sample size of 100 subjects dosed per arm in the 1250 mg and 3500 mg arms, the study has 80% probability of detecting AEs with a rate of 1.2% or greater in these 2 arms, and a 90% probability of detecting AEs occurring with a rate of 2.1% or greater.

CONFIDENTIAL

The information contained herein may not be used, disclosed, or published without the written consent of Biogen MA Inc.

Figure 5: Candidate Models for Dose-Response

[figure not shown]

Table 8: Estimated Sample Size Per Group (Planned)

	Treatment Group				Total
	Placebo	BIIB054 250 mg	BIIB054 1250 mg	BIIB054 3500 mg	
Cohort					
Cohort A	6	6	6	6	24
Cohort B	82	41	82	82	287
Total	88	47	88	88	311

CONFIDENTIAL

The information contained herein may not be used, disclosed, or published without the written consent of Biogen MA Inc.

Table 9: Estimated Sample Size Per Group Based on Actual Enrollment (Before Drop-Outs)

	Treatment Group				
	Placebo	BIIB054 250 mg	BIIB054 1250 mg	BIIB054 3500 mg	Total
Cohort					
Cohort A	8	7	7	7	29
Cohort B	93	47	94	94	328
Total	101	54	101	101	357

Table 10: Estimated Sample Size Per Group Based on Actual Enrollment (After Adjusting for 10% Drop-Out At Week 52)

	Treatment Group				
	Placebo	BIIB054 250 mg	BIIB054 1250 mg	BIIB054 3500 mg	Total
Cohort					
Cohort A	7	6	6	6	25
Cohort B	84	42	84	84	294
Total	91	48	90	90	319

Table 11: Estimated Sample Size Per Group Based on Actual Enrollment (After Adjusting for 15% Drop-Out At Week 72)

	Treatment Group				
	Placebo	BIIB054 250 mg	BIIB054 1250 mg	BIIB054 3500 mg	Total
Cohort					
Cohort A	7	6	6	6	25
Cohort B	79	40	80	80	279
Total	86	46	86	86	304

CONFIDENTIAL

The information contained herein may not be used, disclosed, or published without the written consent of Biogen MA Inc.

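### Section 16.9 assumes a 55% reduction but prints active-arm means of 3.2 and 3.84, which are 60% reductions, so the stated powers rest on contradictory effect sizes

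*Protocol*

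**What the plan says.** All of this is in Protocol Section 16.9 (Sample Size Considerations), in current Version 8 text.

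- Placebo: "the placebo subject's mean and standard deviation (SD) at Week 52 and Week 72 are assumed to be 8.0 (10.64) and 9.6 (13.7) respectively".
- Effect size as a percentage: "Assuming a maximum of 55% reduction in the change from baseline in the active group with maximum response relative to placebo group".
- The same sentence continues with the effect size as means: "the mean (SD) for this active group will be 3.2 (10.64) and 3.84 (13.7) respectively at Week 52 and Week 72".
- Power at Week 52: "average power of approximately 80% to detect the dose-response trend over 1 year of treatment, based on a 2-sided type I error of 0.05".
- Power at Week 72: "approximately 73% of power at the Week 72 analyses, based on a 2-sided type I error of 0.05".
- Combined: "Overall, the sample size in the study will provide approximately 89% power".

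Sample sizes after dropout are in Table 10 (Week 52: 91, 48, 90 and 90 for placebo, 250 mg, 1250 mg and 3500 mg) and Table 11 (Week 72: 86, 46, 86 and 86). The section allows the SAP to change the candidate dose-response models or their parameters. It does not leave the effect size to the SAP; that is stated here, in two forms.

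**The concern.** The percentage and the two means are meant to describe one assumption, and they do not agree. Rounding cannot explain it, since both means are exact multiples of the placebo values at a different percentage.

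This paragraph is the protocol's only statement of the effect the trial is powered to detect on its primary endpoint. The powers of 80% and 73% can belong to only one of the two effect sizes. A reader who takes the only active-arm means supplied will not reproduce the stated powers. Anyone judging a null or borderline result needs to know whether the trial was planned for a 4.4-point or a 4.8-point difference at Week 52, and the text gives both answers.

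**Working it through.** **1. The reductions**

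- From the printed means: 1 − 3.2/8.0 = 60.0% at Week 52; 1 − 3.84/9.6 = 60.0% at Week 72.
- From the stated 55%: 8.0 × 0.45 = 3.6; 9.6 × 0.45 = 4.32.
- Maximum difference from placebo at 55%: 8.0 − 3.6 = 4.4 and 9.6 − 4.32 = 5.28.
- Maximum difference at 60%: 8.0 − 3.2 = 4.8 and 9.6 − 3.84 = 5.76.
- Ratio: 4.8/4.4 = 5.76/5.28 = 1.09.

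**2. Power for the maximum-response arm against placebo**

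This is a simple benchmark that needs no dose-response shape. Normal approximation, two-sided 0.05: power = Φ(difference/SE − 1.960), with SE = SD × √(1/n₁ + 1/n₂).

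- Week 52 (Table 10: 91 and 90; SD 10.64): SE = 10.64 × √(1/91 + 1/90) = 1.582.
- Week 72 (Table 11: 86 and 86; SD 13.7): SE = 13.7 × √(2/86) = 2.089.

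| Timepoint | Reduction | Difference | Difference/SE | Power | Protocol states |
|---|---|---|---|---|---|
| Week 52 | 55% | 4.40 | 2.782 | 79.4% | about 80% |
| Week 52 | 60% | 4.80 | 3.035 | 85.9% | about 80% |
| Week 72 | 55% | 5.28 | 2.527 | 71.5% | about 73% |
| Week 72 | 60% | 5.76 | 2.757 | 78.7% | about 73% |

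**3. Power for the planned MCP-MOD test**

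The candidate parameters are given only in Figure 5, which was not available. So 384 assumed parameter sets were run over Emax, exponential, logistic, linear-in-log and quadratic shapes. Each used optimal contrasts, the Table 10 and 11 sizes and a simulated critical value at one-sided 0.025. In four further sets, this gave practically the same power as two-sided 0.05. Power was averaged over the five shapes.

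| Timepoint | Reduction | Median power | Range over sets |
|---|---|---|---|
| Week 52 | 55% | 81% | 76–85% |
| Week 52 | 60% | 87% | 83–90% |
| Week 72 | 55% | 74% | 69–78% |
| Week 72 | 60% | 81% | 76–84% |

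At 55%, about 48% of the sets came within 2 points of both 80% and 73%. At 60%, none did.

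**4. The overall figure**

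Take powers of 80% and 73% and treat the two test statistics as bivariate normal. The chance of success at one or both timepoints is then 89.3% for a correlation of 0.5, 91.6% for 0.3 and 86.5% for 0.7, with no split of alpha. The stated 89% therefore follows from the 80% and 73% and inherits whichever effect size produced them.

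**5. If the powers had instead been calculated at the printed means**

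This is hypothetical, and steps 2 and 3 point away from it. Scale the noncentrality by 55/60:

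- Week 52: (1.960 + 0.842) × 55/60 = 2.568, so power at a 55% reduction is Φ(0.608) = 73%.
- Week 72: (1.960 + 0.613) × 55/60 = 2.358, so power is Φ(0.398) = 65%.

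**The case against.** The strongest reply accepts the contradiction but argues that it does little harm.

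- **The powers appear sound.** Both reproduce at 55% and neither does at 60%, so the likely fault is two misprinted means. The Version 2 amendment summary used the same placebo value of 8.0 with a 40% reduction, and 3.2 is 8.0 × 0.40, so a 0.40 multiplier may have been left behind. That origin is conjecture.
- **Nothing downstream depends on the means.** Enrollment is complete at 357. The primary analysis does not use the assumed means, and optimal contrasts depend on curve shapes and group sizes, not on the maximum effect. Type I error and trial conduct are untouched.
- **The lower powers in step 5 are a branch the evidence does not support.**

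Most of this stands. It is good reason to expect that the correction will be to the means and that 80%, 73% and 89% will survive on this point. It does not make the text right. The inference to 55% depends on recalculation with assumed shapes, and a reader should not have to reverse-engineer the planning effect from the power. Only the sponsor, who holds the calculation, can settle it.

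**Conclusion.** The contradiction is certain and exact at both timepoints: the text says 55% and the printed means are 60%. It needs no assumption beyond the figures in Section 16.9, and nothing else in the protocol resolves it. The SAP was not available for this check.

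In size, the planned maximum difference is uncertain by 9%. Power differs by about 6 points at Week 52 and 7 points at Week 72 between the two readings. The stated powers agree with 55% and not with the printed means, so the means are probably the error. That last step rests on the pairwise approximation and on assumed MCP-MOD shapes, because the Figure 5 parameters could not be seen. The paragraph has to be corrected because it is the planning basis for the primary endpoint, but there is no sign that the trial is too small for a 55% effect by its own criteria.

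**What to change.** Confirm from the original calculation which effect size was used, then make the paragraph agree with it:

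- **If 55%:** replace 3.2 and 3.84 with 3.6 and 4.32. The stated powers should then stand on this point, subject to a check that all three come from these means.
- **If 60%:** replace 55% with 60% and restate all three powers. As a guide, the pairwise values are 85.9% and 78.7%, and the MCP-MOD medians over the assumed shapes are 87% and 81%. The overall figure must be recalculated from the new pair.

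In either case, derive the Week 52, Week 72 and overall powers from one pair of means. The cost is two corrected means or one percentage, plus a confirmation or re-run of the power calculation. Sample size, conduct and analysis do not change.
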